1. LIST OF ABBREVIATIONS

ADL	Activities of daily living
ADR	Adverse drug reaction
AE	Adverse event
AESI	Adverse event of special interest
ATU	Authorization for use
BCVA	Best Corrected Visual Acuity
BMI	Body mass index
CI	Confidence interval
CR	Complete response
DoR	Duration of response
DoT	Duration of treatment
EAP	Early access program
ECOG	Eastern Cooperative Oncology Group
eCRF	Electronic case report form
EDC	Electronic data capture
EHA	European Hematology Association
EMA	European Medicines Agency
ENCePP	European Network of Centres for Pharmacoepidemiology and Pharmacovigilance
EP	Enrolled population
ESMO	European Society for Medical Oncology
EU	European Union
GCP	Good clinical practice
GSK	GlaxoSmithKline
GVP	Good Pharmaco Vigilance Practice
ICF	Informed consent form
ICH	International Council for Harmonisation of Technical Requirements for Pharmaceuticals for Human Use
IEC	Independent ethics committee
Ig	Immunoglobulin
IMWG	International Myeloma Working Group
IRB	Institutional review board
ISS	International Staging System
kg/m ²	Kilogram per meter square
KM	Kaplan-Meier
KVA	Keratopathy and Visual Acuity
mAB	Monoclonal antibody
MEC	Microcystic-like epithelial changes
MedDRA	Medical Dictionary for Regulatory Activities
mg/kg	Milligram per kilogram
MM	Multiple myeloma
NCCN	National Comprehensive Cancer Network
NCI CTCAE	National Cancer Institute Common Terminology Criteria for Adverse Events

NPP	Named Patient Program
ORR	Overall response rate
OS	Overall survival
PASS	Post-authorisation safety study
PD	Progressive disease
PFS	Progression-free survival
PI	Proteasome inhibitor
PR	Partial response
PT	Preferred term
RMP	Risk management plan
RRMM	Relapsed or refractory MM
rwPFS	Real-world progression-free survival
SAE	Serious adverse event
SAP	Statistical analysis plan
sCR	Stringent complete response
SMA	Site management associate
SMP	Safety management plan
SmPC	Summary of product characteristics
SOC	System organ class
SP	Safety population
US	United States
USPI	US prescribing information
VEO	Value, Evidence and Outcomes
VGPR	Very good partial response
WHO	World Health Organization

TRADEMARK INFORMATION

Trademarks of the GlaxoSmithKline group of companies
BLENREP

Trademarks not owned by the GlaxoSmithKline group of companies
EU PAS
SAS

3. ABSTRACT

3.1. Title

BLNREP™ Effectiveness and Safety in Multiple Myeloma (BEaMM) – Real-World Evidence on Patients Taking Belantamab Mafodotin in Europe

Version 1.921 Apr 2022, PPD [REDACTED], GlaxoSmithKline & PPD [REDACTED], Syneos Health

3.2. Rationale and background

Multiple myeloma (MM) is a rare and incurable haematological malignancy which typically affects adults 60 years of age and older. Current MM therapies include glucocorticoids, chemotherapy, proteasome inhibitors (PIs), immunomodulatory agents and monoclonal antibodies (mAbs, e.g., daratumumab). Since the approval of daratumumab, MM patients have emerged who are refractory to at least one proteasome inhibitor (PI), one immunomodulatory agent and one anti-CD38 monoclonal antibody (mAb). There is a clear unmet medical need for new therapies among patients with relapsed or refractory MM (RRMM) as current treatment options are very limited with a median overall survival (OS) of approximately 7 to 10 months (Gandhi, 2019).

Belantamab mafodotin (BLNREP™) is a first in-class anti-B-cell maturation antigen therapy approved for use in the United States (US) and European Union (EU) based on data from the pivotal Phase II DREAMM-2 study (Study 205678) (Lonial, 2020; Lonial, 2021a).

In the EU, belantamab mafodotin was granted a Conditional Marketing Authorisation on 25 August 2020 for the treatment of MM in adult patients who have received at least four prior therapies and whose disease is refractory to at least one PI, one immunomodulatory agent, and an anti-CD38 mAb, and who have demonstrated disease progression on the last therapy. Because of the risk of ocular toxicity, the European Medicines Agency (EMA) required additional monitoring and additional risk minimisation measures in the form of educational materials for prescribers and patients as detailed in the Risk Management Plan (RMP) (Summary RMP, 2021). The goal of the EU RMP is to mitigate the risk of ocular toxicity of belantamab mafodotin by educating prescribers and patients. The EU Summary of Product Characteristics (SmPC) states ophthalmic examinations should be performed at baseline, before initiation of each of the subsequent 3 treatment cycles, and during treatment as clinically indicated (BLNREP SmPC, 2021).

To better understand the real-world management of RRMM patients exposed to belantamab mafodotin and the occurrence of ocular toxicity in routine clinical practice, this study aims to evaluate the real-world use, safety and effectiveness of belantamab mafodotin in RRMM patients in Europe.

3.3. Research question and Objective(s)

The purpose of this study is to collect real-world data on the use, safety and effectiveness of belantamab mafodotin in RRMM patients in Europe.

Objectives	Description
Primary Objective	Characterize RRMM patients treated with belantamab mafodotin per routine clinical care in terms of demographics, disease status, clinical characteristics and treatment history overall and by line of treatment)
Key Secondary Objectives	
 • Characterize patients with ocular AEs of special interest (AESIs) by belantamab mafodotin treatment, ophthalmic disease history and ocular AESI type, duration and severity (overall and by line of treatment) • Describe frequency and timing of ophthalmic monitoring visits relative to belantamab mafodotin administration (for each cycle; overall and by line of treatment, occurrence of ocular AESIs as well as treatment dose and frequency)
Other Secondary Objectives	
 • Assess the incidence of ocular AESIs (overall and by line of treatment) and their impact on treatment discontinuation, interruption/delay, or dose modifications (overall and by line of treatment, comorbidity, ocular AESI type and severity as well as treatment dose and frequency) • Evaluate persistence and adherence with belantamab mafodotin • Describe reasons for treatment discontinuation • Describe the duration and reasons of treatment interruptions/ delays, or dose modifications • Evaluate effectiveness in terms of disease response to treatment, duration of response (DoR), duration of treatment (DoT), real-world progression-free survival (rwPFS) and overall survival (OS)

3.4. Study Design

This multinational, multisite, non-interventional study aims to collect real-world data on the use, safety and effectiveness of belantamab mafodotin in RRMM patients from Europe. Background data at the time of the first dose of belantamab mafodotin (i.e., demographics, disease status, clinical characteristics and treatment history) will be collected to characterize RRMM patients treated with belantamab mafodotin per routine clinical care. In addition, data will be collected on the occurrence, duration and management of ocular AESIs, the frequency and timing of ophthalmic examinations, persistence and adherence with belantamab mafodotin, treatment discontinuations, interruptions/delays and decreased dosing, and effectiveness in terms of treatment response and survival.

Data will be analysed from approximately 150 RRMM patients from sites in selected countries in Europe. Eligible RRMM patients from EU sites who are due to receive their first dose of belantamab mafodotin will be consecutively invited for study enrolment by haematologists and/or oncologists affiliated with investigator sites participating in this study. In the event the enrolment rate after study start is too low to meet the expected 150 RRMM patients within the planned enrolment timeframe, eligible RRMM patients from sites who received their first belantamab mafodotin dose before study enrolment will be

invited for study participation.. As the study is non-interventional, the decision to treat patients with belantamab mafodotin will be made prior to and independent from the decision to enrol patients into the study, and baseline and follow-up assessments will be in accordance with local standard medical care.

After obtaining informed consent, data will be collected into an electronic case report form (eCRF) directly during prospective follow-up or will be collected retrospectively from medical records, where applicable, from the time of the first dose of belantamab mafodotin to the end of follow-up at 15 months, study discontinuation for any reason, informed consent withdrawal or death; whichever comes first. The Investigator will follow ocular AESIs until resolved or until the last study visit of the patient.

The total study duration is estimated to be a maximum of two years and three months per site based on an estimated study enrolment period of 12 months and a follow-up period of 15 months.

3.5. Population

It is planned to include approximately 150 RRMM patients from sites in selected countries across Europe, from patients who are due to receive belantamab mafodotin as part of routine clinical care after study enrolment.

Inclusion Criteria:

A patient who meets **all** of the following criteria is eligible for inclusion:

- Written informed consent
- Male or female, ≥ 18 years of age at the start of belantamab mafodotin treatment
- Confirmed diagnosis of RRMM
- Received (first dose up to three months before study enrolment; if deemed required based on enrolment rate) or due to receive belantamab mafodotin treatment per routine clinical care by an oncologist or haematologist consistent with the approved labelling

Exclusion Criteria:

A patient who meets **any** of the following criteria is not eligible for inclusion:

- Concurrent enrolment in an interventional clinical trial involving either an investigational medicinal product (including belantamab mafodotin) or medical device
- Concurrent enrolment in a belantamab mafodotin early access program (EAP), Named Patient Program (NPP) or temporary authorization for use (ATU) program

3.6. Variables

- Demographics, disease status, clinical characteristics and treatment history data
- Belantamab mafodotin treatment details including dose, duration, discontinuations, interruptions/delays and dose changes
- Ophthalmic examination details (e.g. type, frequency, date) and results

- Information on all ocular AESIs, including severity, seriousness, duration, relationship to and impact on daily living, belantamab mafodotin treatment and actions taken
- Treatment effectiveness data including survival status, progression and tumour response according to International Myeloma Working Group (IMWG) criteria if feasible or to local standard practice

3.7. Data sources

Data will be collected by Investigators or their designees (i.e., haematologists, oncologists and ophthalmologists) directly into the eCRF during prospective follow-up from patients enrolled into this study from sites selected countries across Europe. Countries and sites in Europe will be included based on the expected belantamab mafodotin market uptake and site availability. In addition, data will be collected retrospectively from medical records from patients enrolled into this study who received their first belantamab mafodotin dose up to three months before study enrolment, if necessary.

3.8. Study size

A sample size of 150 evaluable RRMM patients is planned for this study.

3.9. Data analysis

Analysis populations:

Two analysis populations will be defined:

- Enrolled Population (EP) - All patients for whom written informed consent has been obtained
- Safety Population (SP) - All patients in the EP who received at least one dose of belantamab mafodotin. The SP will be used for descriptive, safety and effectiveness analyses

Statistical Methods:

For the primary objective, characteristics of RRMM patients treated with belantamab mafodotin per routine clinical care will be described for the SP (overall and by line of treatment). Characteristics to be described include demographics, disease status, clinical characteristics and treatment history collected before or at the time of the first dose.

For the secondary objectives, the following will be described for the SP (overall and by line of treatment):

- Treatment dose, duration, persistence and adherence
- Ocular AESIs during the study period:
- Number, proportions, co-occurrence, time to (specific) ocular AESIs and incidence rate (at the patient and event level); overall and by System Organ Class (SOC) and Preferred Term (PT) terms (Medical Dictionary for Regulatory Activities [MedDRA] classification) and according to severity, grade, seriousness, action taken, duration, impact on daily living and relationship to treatment as well as treatment dose and frequency

- Number, proportion, severity, grade, seriousness and duration of ocular AESIs by ophthalmic monitoring frequency, type(s) and timing relative to administration
- Severity, grade, seriousness and duration of ocular AESIs by their treatment impact (e.g., dose changes, duration of interruptions/delays, discontinuation), use of artificial tears and dry eye comorbidity
- Number and proportions of patients with dose reductions, interruptions/delays or discontinuing treatment due to an ocular AESI during the study period: overall and by comorbidity. This will include the description of the timing and dose of treatment re-introductions and the duration of dose reductions and interruptions/delays
- Treatment response (e.g., complete response [CR], very good partial response [VGPR]; partial response [PR]; according to IMWG criteria if feasible or to local standard practice) and time to events (i.e., death, progression, discontinuation)

Continuous variables will be described (distribution) by their mean, standard deviation, median, first and third quartile (Q1 and Q3), extreme values (minimum and maximum) and the number of non-missing and missing data. Categorical variables will be described using frequency counts and percentages.

Data analysis:

The following measures will be reported:

- Exposure-adjusted incidence and event rates with 95% confidence intervals of ocular AESIs (i.e., at the patient level and the event level): overall and by SOC and PT terms (MedDRA classification).
- Median, 95% confidence intervals (CIs) and 25th and 75th percentiles using the Kaplan-Meier (KM) method for time to event outcomes (i.e., OS, rwPFS, DoR, time to discontinuation, time to first [specific] ocular AESI)
- OS rates with 95% CIs at specified time points, including 12- and 15-months of follow-up
- Overall response rate (ORR) with 95% CIs calculated based on the exact binomial distribution (Clopper-Pearson method).

Additional subgroup analyses will be conducted for primary and secondary outcomes by key patient characteristics (e.g., Eastern Cooperative Oncology Group [ECOG] performance status, age groups at the index date, MM subtype, retrospective vs prospective data, and presence or absence of ocular AESIs) when deemed applicable and feasible, as described in the Statistical Analysis Plan (SAP).

Details of interim analyses will be described in the SAP.

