6. RATIONALE AND BACKGROUND

6.1. Background

Multiple myeloma (MM) is a rare and incurable haematological malignancy which typically affects adults 60 years of age and older. It is the second most common haematological malignancy (after non-Hodgkin's lymphoma), representing 1% of all cancers and 2% of all cancer deaths. In 2020, the estimated annual, age-standardised, worldwide MM incidence rate was 1.8 per 100,000 (GLOBOCAN, 2020).

Current MM therapies include glucocorticoids (e.g., dexamethasone), chemotherapy, proteasome inhibitors (PIs, e.g., bortezomib), immunomodulatory agents (e.g., thalidomide, lenalidomide and pomalidomide), monoclonal antibodies (mAbs, e.g., daratumumab, isatuximab and elotuzumab) and the histone deacetylase inhibitor panobinostat. Since the approval of daratumumab, MM patients have emerged who are refractory to at least one PI, one immunomodulatory agent and one anti-CD38 mAb. There is a clear unmet medical need for new therapies among patients with relapsed or refractory MM (RRMM) as current treatment options are very limited with a median overall survival (OS) of approximately 7 to 10 months (Gandhi, 2019).

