Belantamab mafodotin (BLENREP™) is a first in-class anti-B-cell maturation antigen therapy approved for use in the United States (US) and European Union (EU) based on data from the pivotal Phase II DREAMM-2 study (Study 205678) (Lonial, 2020; Lonial, 2021a). DREAMM-2 is a phase II, open label, randomized, two-arm study investigating the efficacy and safety of two doses of belantamab mafodotin (3.4 mg/kg vs. 2.5 mg/kg) in participants with MM who had ≥ 3 prior lines of treatment, were refractory to a proteasome inhibitor and an immunomodulatory agent and had failed an anti-CD38 antibody (Lonial, 2020; Lonial, 2021a). DREAMM-2 results after 13-month follow-up showed an overall response rate (ORR) for the 97 patients who received the registration dose (i.e., 2.5 mg/kg) of 32% (97.5% confidence interval [CI], 21.7-43.6) with 58% of responders achieving a very good partial response (VGPR) or better, including 2 stringent complete responses (sCRs) and 5 CRs (Lonial, 2021a). Median estimated duration of response (DoR), OS, and progression-free survival (PFS) were 11.0 months (95% CI, 4.2 months to not reached), 13.7 months (95% CI, 9.9 months to not reached), and 2.8 months (95% CI, 1.6-3.6 months), respectively (Lonial, 2021a). The most frequent adverse reactions ($\geq 30\%$) reported from 95 patients in DREAMM-2 who received belantamab mafodotin 2.5 mg/kg were keratopathy (71%) and thrombocytopenia (38%). The most commonly reported serious adverse reactions were pneumonia (7%), pyrexia (7%) and infusion-related reactions (3%). Permanent discontinuation due to an adverse reaction occurred in 9% of patients who received belantamab mafodotin with 3% related to ocular adverse reactions.

In the EU, belantamab mafodotin was granted a Conditional Marketing Authorisation on 25 August 2020 for the treatment of MM in adult patients who have received at least four prior therapies and whose disease is refractory to at least one PI, one immunomodulatory agent, and an anti-CD38 mAb, and who have demonstrated disease progression on the last therapy. Because of the risk of ocular toxicity, the European Medicines Agency (EMA) required additional monitoring and additional risk minimisation measures in the

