8.3.5. Safety

All ocular AESIs that occur during and/or after administration of belantamab mafodotin will be recorded regardless of a causal relationship to belantamab mafodotin. Data shown in [Table 5](#) will be collected for any ocular AESI (serious or non-serious) until the end of follow-up at 15 months, study discontinuation for any reason, informed consent withdrawal or death; whichever comes first.

Table 5 Ocular Adverse Events of Special Interest

Variable	Definition	Timing
Date(s) ocular AESI(s)	Date of onset of each ocular AESIs	Index date and post-index period
Ocular AESI type	Categorical variable: type of ocular AESI* categorized by: 
 • Keratopathy** • Blurred vision events# • Dry eye events## • Photophobia • Eye irritation • Ulcerative keratitis • Infective keratitis • Corneal erosion/defect • Other 	Index date and post-index period
Ocular AESI severity at onset	Categorical variable: NCI CTCAE Version 5.0 grading: 
 • Grade 1 • Grade 2 • Grade 3 • Grade 4 • Grade 5 KVA scale grade (see ANNEX 2): 
 • Normal • Grade 1 • Grade 2 • Grade 3 • Grade 4 	Index date and post-index period
Ocular AESI severity increase after onset	Categorical variable: 
 • Yes – specify highest grade • No 	Index date and post-index period
Ocular AESI seriousness at onset	Categorical variable: 
 • Fatal • Life-threatening • Persistent or significant disability/incapacity • Inpatient (or prolongation of existing) hospitalization • Medically important event • None of the above 	Index date and post-index period
Ocular AESI seriousness increase after onset	Categorical variable: 
 • Yes – specify most serious event • No 	Index date and post-index period
Ocular AESI impact on daily living	Categorical variable (e.g., need for caregiver support, eye irritation/pain, driving impairment, reading impairment)	Index date and post-index period
Action taken	Categorical variable: 
 • Concomitant medication@ and other mitigation strategies (e.g., bandage contact lenses) • Belantamab mafodotin treatment change 
 • Dose decrease • Treatment interruption/delay 	Index date and post-index period

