8.7.2.3. Analysis of Key Secondary Objectives

For the key secondary objectives, the following will be described for the SP (overall and by line of treatment) during active treatment exposure periods:

- Average cycle dose (sum of all doses divided by total number of administrations per patient)
- Frequency and timing of ophthalmic monitoring relative to belantamab mafodotin administration for each cycle (type(s), number of examinations; overall and according to monitoring before and after the occurrence of ocular AESIs as well as treatment dose and frequency)
- Ocular AESIs in RRMM patients exposed to belantamab mafodotin occurring during the study period:
 - Number, proportions, co-occurrence and time to (specific) ocular AESIs; overall and by System Organ Class (SOC) and Preferred Term (PT) terms (MedDRA classification) and according to severity, grade, seriousness, action taken, duration, impact on daily living and relationship to treatment as well as treatment dose and frequency
 - Number, proportion, severity, grade, seriousness and duration of ocular AESIs by ophthalmic monitoring frequency, type(s) and timing relative to administration
 - Severity, grade, seriousness and duration of ocular AESIs by their treatment impact (e.g., dose changes, duration of interruptions/delays, discontinuation), use of artificial tears and dry eye comorbidity

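### Kaplan-Meier percentiles for time to first ocular AESI censor AESI-free deaths, so percentiles near the plateau come out too early or appear when they are never reached

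*Protocol*

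**What the plan says.** Protocol section 3.9 plans Kaplan-Meier medians, with 95% CIs, and quartiles. The outcomes covered are listed there as follows: "for time to event outcomes (i.e., OS, rwPFS, DoR, time to discontinuation, time to first [specific] ocular AESI". Section 8.7.2.3 lists the same outcome among the key secondary analyses ("Number, proportions, co-occurrence and time to (specific) ocular AESIs; overall and by System Organ Class (SOC) and Preferred Term (PT) terms") without naming a method.

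By the definitions in section 8.3.1, death is the event for OS and part of the event for rwPFS and DoR. It is not part of the ocular AESI outcome. Under section 8.3.5, AESI data are collected "until the end of follow-up at 15 months, study discontinuation for any reason, informed consent withdrawal or death; whichever comes first". The Protocol names no cumulative-incidence or competing-risk method.

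On expected mortality, section 6.1 cites a pivotal-study median OS of "13.7 months (95% CI, 9.9 months to not reached") and, with existing options, a "median overall survival (OS) of approximately 7 to 10 months". Follow-up is 15 months.

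**The concern.** A Kaplan-Meier curve for a single non-fatal event treats each censored patient as someone who could still have the event later. That is reasonable for a patient who reaches month 15, but not for one who has died. With AESI-free deaths censored, the curve describes AESI onset in a hypothetical cohort where nobody dies. One minus that curve is never below the actual cumulative incidence, so its percentiles are never later than the actual ones.

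The percentiles are the planned output, for each specific AESI as well as for any AESI. The report could state a median or upper quartile for an ocular AESI that fewer than 50% or 75% of patients ever have. Characterising ocular AESIs is a key secondary objective, so the timing figures should describe the treated cohort.

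**Working it through.** The Protocol gives no figure for this curve, so there is none to reproduce. The check compares the two estimators.

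**Inputs from the Protocol.** Follow-up 15 months (8.3.1). Median OS 13.7 months, or 7 to 10 with existing options (6.1). Keratopathy 71% in the pivotal study (6.1). Median PFS 2.8 months (6.1). Exposure window reaching to last dose + 70 days (8.3.1).

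**Assumptions.** Independent hazards; exponential survival; AESI hazard λ chosen to give a stated true 15-month risk. The Protocol gives no AESI hazard, so two shapes are used.

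**Formulas, constant hazards** (death hazard μ = ln 2 / median OS):
- Cumulative incidence: λ/(λ+μ) × [1 − exp(−(λ+μ)t)], with plateau λ/(λ+μ).
- Kaplan-Meier with deaths censored: 1 − exp(−λt).
- Kaplan-Meier p-th percentile: −ln(1−p)/λ.
- Cumulative-incidence p-th percentile: −ln[1 − p(λ+μ)/λ]/(λ+μ). It exists only if p is below the plateau.

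**Deaths.** μ = 0.6931/13.7 = 0.0506 per month. Dead by month 15: 1 − exp(−0.0506 × 15) = 53%. With median OS of 10 and 7 months: 65% and 77%.

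**Shape 1: constant AESI hazard, median OS 13.7 months**

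| True 15-month risk | λ per month | Percentile | Kaplan-Meier (months) | Cumulative incidence (months) |
|---|---|---|---|---|
| 71% | 0.1495 | 25th | 1.9 | 2.0 |
| 71% | 0.1495 | 50th | 4.6 | 5.5 |
| 71% | 0.1495 | 75th | 9.3 | never |
| 50% | 0.0735 | 25th | 3.9 | 4.4 |
| 50% | 0.0735 | 50th | 9.4 | 15.0 |
| 25% | 0.0285 | 25th | 10.1 | 15.0 |

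For the 71% case, the plateau is 0.1495/(0.1495 + 0.0506) = 74.7%, below 75%, so the upper quartile is never reached even with unlimited follow-up. Kaplan-Meier still returns ln 4/0.1495 = 9.3 months.

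With shorter survival the gap widens. For the 50% case, the Kaplan-Meier median is 8.1 months (OS 10) or 6.4 months (OS 7), against 15.0 in both.

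**Shape 2: AESI hazard only during treatment plus 70 days, median OS 13.7 months** (simulation; treatment time exponential with median 2.8 months, assumed equal to the cited PFS)
- True risk about 71%: median about 2.2 months by Kaplan-Meier against about 2.3 by cumulative incidence. The Kaplan-Meier 75th percentile is about 5.6 months and is never reached. That value is sensitive to the assumed risk, because the curve is flat there: 5.9 months at exactly 71%, 4.7 at 74%.
- True risk 49%: Kaplan-Meier median 6.1 months, although incidence never reaches 50%. The 25th percentile hardly moves: 1.92 against 2.03 months.

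**Very early onset** (71% risk, all hazard in the first 2 to 4 months, OS 13.7): the medians differ by about 0.1 month or less (1.03 against 1.07; 1.91 against 2.04). With a two-month onset period Kaplan-Meier reaches only 73.8%, so neither curve has an upper quartile.

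Shape 1, extended to all 15 months including time off drug, is an upper-end scenario and not one the Protocol supports. Shape 2 is more favourable to the plan.

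**The case against.** **Is the risk of ocular events overstated?** A reader might infer this. The Protocol does not support it. Sections 3.9 and 8.7.2.3 plan the number and proportion of patients with each AESI as crude figures, and 8.7.2.4 adds exposure-adjusted rates. Kaplan-Meier does not enter any of these. Rates at fixed times are planned for OS, not for AESIs. One minus Kaplan-Meier at month 15 would read 89.4% for a true 71% under shape 1, but that is not a listed output. A gap between such a curve and the crude proportion would reflect two different quantities, not a contradiction.

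**For common early events the effect is small.** This stands. At a true risk of 74% under shape 2, the medians are 1.99 and 2.13 months. The difference is below the sampling SD of about 0.25 month at N = 150.

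**Onset is not too early in every sense.** This also stands. Kaplan-Meier percentiles are early against cumulative-incidence percentiles. Against onset among affected patients only, the Kaplan-Meier median is later (4.6 against 3.2 months for the 71% case under shape 1).

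**Leaving the exposure window.** A reader might add that patients leaving exposure are censored too, with a much larger distortion. The lead-in of 8.7.2.3 does describe results "for the SP (overall and by line of treatment) during active treatment exposure periods", but its own AESI bullet and section 3.9 refer to the study period, and sections 8.1 and 8.3.5 collect AESIs after treatment stops. That is an inconsistency to resolve, not an established censoring rule.

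**How firmly is the method fixed?** Kaplan-Meier for AESIs appears only in the abstract (3.9), no censoring rule is written, and the SAP is not at hand. No hypothesis is tested. Even so, 3.9 names the method in an exhaustive list, and for an endpoint without death that method implies censoring AESI-free deaths. A descriptive study still needs percentiles that describe its cohort.

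**Conclusion.** The point holds in a narrow form. The direction is certain: with AESI-free deaths censored, Kaplan-Meier percentiles are never later than cumulative-incidence percentiles.

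The size depends on where the percentile lies. Early percentiles of common, early AESIs move by about 0.1 to 0.2 month, which is negligible. Percentiles near the plateau are materially wrong or should not be reported at all, as with the 75th percentile for an AESI of about 71% risk and the median for one of about 50%.

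These sizes rest on assumed independent hazards, exponential survival and, for shape 2, treatment time equal to the cited PFS. The conclusion does not extend to the crude AESI counts and proportions or to the exposure-adjusted rates. It does not rest on the exposure-window question. This is a low-cost improvement to the reporting of AESI timing, not a threat to the primary objective.

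**What to change.** In section 3.9, take time to first (specific) ocular AESI out of the Kaplan-Meier list. There and in 8.7.2.3, estimate it by Aalen-Johansen cumulative incidence with death as a competing event. Report the median and quartiles from that curve with 95% CIs, or as not reached. Keep Kaplan-Meier for OS, rwPFS and DoR.

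Separately, reconcile the AESI observation window in 8.7.2.3, which names both active exposure periods and the study period. Only if the on-exposure window is kept should end of exposure be a second competing event.

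The cost is a wording change and matching SAP text. No new data are needed, and the method is available in SAS 9.4. The downside is that more percentiles for less common AESIs will read as not reached.
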